6.1. Appendix 1: Demographic and Baseline Characteristics

The patient's year of birth, sex, weight, height, smoking habits, previous biologic treatment, and other demographic characteristics are collected at the screening visit. Age and body mass index will be calculated.

Only the year of birth is collected at screening. For the purpose of age calculation, the month and day of birth will be imputed as July 01, of the year of birth. Age is computed as follows;

$$\text{Age} = (\text{Informed Consent Date} - \text{Date of Birth} + 1) / 365.25.$$

Demographic and baseline characteristics (including age, gender, race, and ethnicity) will be summarized for each treatment group.

Certain characteristics, that are collected at baseline or after baseline but not summarized in the demographic summary, will be reported as a listing.

No inferential analysis for the comparability of baseline covariates across treatment groups will be performed.

6.2. Appendix 2: Preexisting Conditions

Preexisting condition is defined the condition/event recorded on the Preexisting Conditions and Medical History electronic case report form (eCRF) page with a start date prior to the date of informed consent, and no end date (that is, the event is ongoing) or an end date on or after the date of informed consent. In addition, the AEs occurring prior to first dose are also included.

Notice if a preexisting condition worsens in severity on or after the date of informed consent, it will be recorded as an AE on the AE eCRF page with the date of worsening as the start date. The number and percentage of patients with preexisting conditions will be summarized by treatment group using the MedDRA Preferred Term (PT) nested within System Organ Class (SOC). Summaries will be performed for the ITT population.

6.3. Appendix 3: Treatment Compliance

Study treatment administration and compliance will be listed for all entered patients. The number and percentage of patients who are treatment compliant by week (that is, at each injection time point) will be summarized by treatment group for each treatment period.

No patient will be excluded from the ITT population as a consequence of significant noncompliance.

Participants who are noncompliant with treatment will be listed by treatment group.

No analyses are planned to assess treatment compliance.

6.4. Appendix 4: Prior and Concomitant Therapy

Prior and concomitant medications will be summarized by treatment group and will be classified into anatomical therapeutic chemical (ATC) drug classes using the latest version of the World Health Organization (WHO) drug dictionary. Medication start and stop dates will be compared to

the date of first dose of treatment in each treatment period to allow medications to be classified as Concomitant for each treatment period.

Prior medications are those medications that start and stop prior to the date of first dose of study treatment. Concomitant medications are those medications that start before, on or after the first day of study treatment of the defined treatment period and continue into the treatment period.

6.5. Appendix 5: Clinical Trial Registry Analyses

Additional analyses will be performed for the purpose of fulfilling the Clinical Trial Registry (CTR) requirements.

Analyses provided for the CTR requirements include the following:

Summary of adverse events, provided as a dataset which will be converted to an XML file. Both Serious Adverse Events and ‘Other’ Adverse Events are summarized: by treatment group, by MedDRA preferred term.

- An adverse event is considered ‘Serious’ whether or not it is a treatment emergent adverse event (TEAE).
- An adverse event is considered in the ‘Other’ category if it is both a TEAE and is not serious. For each Serious AE and ‘Other’ AE, for each term and treatment group, the following are provided:
 - the number of participants at risk of an event
 - the number of participants who experienced each event term
 - the number of events experienced.
- Consistent with www.ClinicalTrials.gov requirements, ‘Other’ AEs that occur in fewer than 5% of patients/subjects in every treatment group may not be included if a 5% threshold is chosen (5% is the minimum threshold).

AE reporting is consistent with other document disclosures for example, the CSR, manuscripts, and so forth.

6.6. Appendix 6: Daily Diary Calculations

Weekly summary measures of daily diary data will be created for each patient. The 7-day period associated with each week will be defined using a visit centric approach. The table below displays the interval for each week:

Week (Visit)	Start Day ^a	End Day ^a
Baseline	Week 0 Visit Date – 7	Week 0 Visit Date – 1
Week 1 (V3)	Max(Week 0 Visit Date, Week 1 Visit Date – 7)	Week 1 Visit Date – 1
Week 2 (V4)	Max(Week 1 Visit Date , Week 2 Visit Date – 7)	Week 2 Visit Date – 1

Week 3	Max (Week 2 Visit Date, Week 4 Visit Date – 14)	Week 4 Visit Date – 8
Week 4 (V5)	Max (Week 2 Visit Date, Week 4 Visit Date – 7)	Week 4 Visit Date – 1
Week 5	Max (Week 4 Visit Date, Week 6 Visit Date – 14)	Week 6 Visit Date – 8
Week 6 (V6)	Max (Week 4 Visit Date, Week 6 Visit Date – 7)	Week 6 Visit Date – 1
Week 7	Max (Week 6 Visit Date, Week 8 Visit Date – 14)	Week 8 Visit Date – 8
Week 8 (V7)	Max (Week 6 Visit Date, Week 8 Visit Date – 7)	Week 8 Visit Date – 1
Week 9	Max (Week 8 Visit Date, Week 10 Visit Date – 14)	Week 10 Visit Date – 8
Week 10 (V8)	Max (Week 8 Visit Date, Week 10 Visit Date – 7)	Week 10 Visit Date – 1
Week 11	Max (Week 10 Visit Date, Week 12 Visit Date – 14)	Week 12 Visit Date – 8
Week 12 (V9)	Max (Week 10 Visit Date, Week 12 Visit Date – 7)	Week 12 Visit Date – 1
Week 13	Max (Week 12 Visit Date, Week 14 Visit Date – 14)	Week 14 Visit Date – 8
Week 14 (V10)	Max (Week 12 Visit Date, Week 14 Visit Date – 7)	Week 14 Visit Date – 1
Week 15	Max (Week 14 Visit Date, Week 16 Visit Date – 14)	Week 16 Visit Date – 8
Week 16 (V11)	Max (Week 14 Visit Date, Week 16 Visit Date – 7)	Week 16 Visit Date – 1
Week 17	Max (Week 16 Visit Date, Week 18 Visit Date – 14)	Week 18 Visit Date – 8
Week 18 (V12)	Max (Week 16 Visit Date, Week 18 Visit Date – 7)	Week 18 Visit Date – 1
Week 19	Max (Week 18 Visit Date, Week 20 Visit Date – 14)	Week 20 Visit Date – 8
Week 20 (V13)	Max (Week 18 Visit Date, Week 20 Visit Date – 7)	Week 20 Visit Date – 1
Week 21	Max (Week 20 Visit Date, Week 22 Visit Date – 14)	Week 22 Visit Date – 8
Week 22 (V14)	Max (Week 20 Visit Date, Week 22 Visit Date – 7)	Week 22 Visit Date – 1
Week 23	Max (Week 22 Visit Date, Week 24 Visit Date – 14)	Week 24 Visit Date – 8
Week 24 (V15)	Max (Week 22 Visit Date, Week 24 Visit Date – 7)	Week 24 Visit Date – 1
Week 25	Max (Week 24 Visit Date, Week 26 Visit Date – 14)	Week 26 Visit Date – 8
Week 26 (V16)	Max (Week 24 Visit Date, Week 26 Visit Date – 7)	Week 26 Visit Date – 1
Week 27	Max(Week 26 Visit Date, Week 28 Visit Date – 14)	Week 28 Visit Date – 1
Week 28 (V17)	Max(Week 26 Visit Date , Week 28 Visit Date – 7)	Week 28 Visit Date – 1

Week 29	Max (Week 28 Visit Date, Week 30 Visit Date – 14)	Week 30 Visit Date – 8
Week 30 (V18)	Max (Week 28 Visit Date, Week 30 Visit Date – 7)	Week 30 Visit Date – 1
Week 31	Max (Week 30 Visit Date, Week 32 Visit Date – 14)	Week 32 Visit Date – 8
Week 32 (V19)	Max (Week 30 Visit Date, Week 32 Visit Date – 7)	Week 32 Visit Date – 1
Week 33	Max (Week 32 Visit Date, Week 34 Visit Date – 14)	Week 34 Visit Date – 8
Week 34 (V20)	Max (Week 32 Visit Date, Week 34 Visit Date – 7)	Week 34 Visit Date – 1
Week 35	Max (Week 34 Visit Date, Week 36 Visit Date – 14)	Week 36 Visit Date – 8
Week 36 (V21)	Max (Week 34 Visit Date, Week 36 Visit Date – 7)	Week 36 Visit Date – 1
Week 37	Max (Week 36 Visit Date, Week 38 Visit Date – 14)	Week 38 Visit Date – 8
Week 38 (V22)	Max (Week 36 Visit Date, Week 38 Visit Date – 7)	Week 38 Visit Date – 1
Week 39	Max (Week 38 Visit Date, Week 40 Visit Date – 14)	Week 40 Visit Date – 8
Week 40 (V23)	Max (Week 38 Visit Date, Week 40 Visit Date – 7)	Week 40 Visit Date – 1
Week 41	Max (Week 40 Visit Date, Week 42 Visit Date – 14)	Week 42 Visit Date – 8
Week 42 (V24)	Max (Week 40 Visit Date, Week 42 Visit Date – 7)	Week 42 Visit Date – 1
Week 43	Max (Week 42 Visit Date, Week 44 Visit Date – 14)	Week 44 Visit Date – 8
Week 44 (V25)	Max (Week 42 Visit Date, Week 44 Visit Date – 7)	Week 44 Visit Date – 1
Week 45	Max (Week 44 Visit Date, Week 46 Visit Date – 14)	Week 46 Visit Date – 8
Week 46 (V26)	Max (Week 44 Visit Date, Week 46 Visit Date – 7)	Week 46 Visit Date – 1
Week 47	Max (Week 46 Visit Date, Week 48 Visit Date – 14)	Week 48 Visit Date – 8
Week 48 (V27)	Max (Week 46 Visit Date, Week 48 Visit Date – 7)	Week 48 Visit Date – 1
Week 49	Max (Week 48 Visit Date, Week 50 Visit Date – 14)	Week 50 Visit Date – 8
Week 50 (V28)	Max (Week 48 Visit Date, Week 50 Visit Date – 7)	Week 50 Visit Date – 1
Week 51	Max (Week 50 Visit Date, Week 52 Visit Date – 14)	Week 52 Visit Date – 8
Week 52 (V29)	Max (Week 50 Visit Date, Week 52 Visit Date – 7)	Week 52 Visit Date – 1

Abbreviations: V = Visit.

^a If End Day < Start Day, do not assign specified visit week. Visit date will be calculated by selecting the first date from the following list (i.e., first in list order): (1) date of earliest bowel preparation if bowel preparation date is available, (2) date of endoscopy if endoscopy was performed, (3) date of treatment if treatment was given, (4) office visit date if available, or (5) imputed date of visit center of the protocol-defined window for that visit. The screening endoscopy is assumed to be associated with the Week 0 visit.

For the Mayo SF and RB subscores, the most recent 3 nonmissing days of the 7-day period in the table above will be averaged and rounded to the nearest integer to calculate the weekly score for each patient. Patients with less than 3 measurements in the 7 day period will be considered missing.

For the Bristol Stool Scale the worst (i.e. maximum) of the available measures during the 7 period in the table above will be used to calculate a weekly score for each patient. If fewer than 4 days are available (i.e., not missing), the patient will be considered to be missing data for that week.

For all other daily diary measures, all available days of the 7 days will be averaged and rounded to the nearest integer to calculate the weekly score for each patient. If fewer than 4 days are available (i.e., not missing), the patient will be considered to be missing data for that week.

If multiple diary assessments on a single day are present, use the earliest nonmissing assessment. Data from the following days will be considered missing: (i) days when patients receive bowel preparation, (ii) the day of an endoscopy, and (iii) two days after an endoscopy.

If the baseline assessment is missing per the above rules, the first available postbaseline assessment starting with Week 1 will be used to impute the baseline so that the patient can be included in the analysis.

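### Two rows of the SAP diary-window table miss their target: Week 27 covers up to 14 days and contains all of Week 28, and Week 1 can include up to 3 pre-dose days (minor)

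*SAP*

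**What the plan says.** SAP 6.6 derives weekly diary scores from a table of start and end days. Its opening rule is "The 7-day period associated with each week will be defined using a visit centric approach".

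- **Week 27.** The start day is "Max(Week 26 Visit Date, Week 28 Visit Date – 14" and the end day is "Week 28 Visit Date – 1". The Week 28 row starts at "Max(Week 26 Visit Date , Week 28 Visit Date – 7" and has the same end day. The next odd-week row, Week 29, ends at "Week 30 Visit Date – 8".
- **Week 1.** The start day is "Max(Week 0 Visit Date, Week 1 Visit Date – 7". The footnote takes a visit date from a ranked list in which bowel preparation and endoscopy come ahead of the treatment date. It adds: "The screening endoscopy is assumed to be associated with the Week 0 visit".
- **Scoring.** For stool frequency (SF) and rectal bleeding (RB), "the most recent 3 nonmissing days of the 7-day period in the table above will be averaged". The Bristol Stool Scale takes the window maximum. The other five diary items take the mean of the available days. These last six items need at least 4 nonmissing days. Bowel preparation days, the endoscopy day and the two days after it count as missing.

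In the protocol's Schedule of Activities (Table 1), the screening endoscopy may be up to 14 days before randomization, the first dose is at Visit 2 (Day 1), and Visit 3 is Day 8 ±3 with no dose.

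**The concern.** The table is a programming specification. SAP 4.4.2 calls for diary outcomes to be summarized by time point and plotted over time, and SAP 4.1.1 allows comparisons with placebo at Week 12 and at other suitable time points. A programmer who follows the Week 27 row literally produces a Week 27 value that largely or wholly restates Week 28. A programmer who silently corrects it departs from the approved plan. The Week 1 row can mix untreated days into the first on-treatment diary time point.

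**Working it through.** Notation: W0, W1, W26 and W28 are the visit dates under the SAP 6.6 footnote. Window length = end − start + 1.

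**Plan's own figure.** With every visit on its nominal day, each row of the table gives the stated 7 days, except Week 27.

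**Week 27**

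- Inputs: W26 = Day 183 and W28 = Day 197, each ±3 (protocol Tables 2 and 3).
- Start = max(183, 197 − 14) = Day 183. End = 197 − 1 = Day 196. Length = 196 − 183 + 1 = 14 days.
- Week 28: start = max(183, 197 − 7) = Day 190, end = Day 196. All 7 days lie inside Week 27.
- Within tolerance, length = min(W28 − W26, 14). The gap between visits runs from 8 to 20 days, so the length runs from 8 to 14.
- Containment holds in all 49 combinations of visit days: the end days are identical, and max(W26, W28 − 14) can never exceed max(W26, W28 − 7).
- Comparison: there are (51 − 3)/2 + 1 = 25 odd-week rows from Week 3 to Week 51. The other 24 end 8 days before the next visit. On that pattern Week 27 would be Days 183–189, which is 7 days with no overlap.

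Effect on the scores:

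- SF and RB at Week 27 equal Week 28 whenever Week 28 has at least 3 nonmissing days.
- Bristol becomes a maximum over up to 14 days, and the five averaged items become means over up to 14 days.
- The 4-day completeness rule can be bypassed for extension participants, who have a Week 26 endoscopy. Take bowel preparation on Day 183 and endoscopy on Day 184, so that Days 183–186 are missing. A 7-day window (183–189) leaves 7 − 4 = 3 usable days, and the six items would be missing. The printed window leaves up to 14 − 4 = 10, and a value is assigned.

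**Week 1**

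- Inputs: Visit 3 on Day k, with k from 5 to 11; W0 lies D days before Day 1.
- W1 − 7 falls 8 − k days before Day 1. For k below 8, the number of pre-dose days in the window is min(8 − k, D). For k of 8 or more it is 0.

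| Visit 3 | Pre-dose days if D ≥ 3 | Share of 7 days |
|---|---|---|
| Day 5 | 3 | 43% |
| Day 6 | 2 | 29% |
| Day 7 | 1 | 14% |
| Day 8 or later | 0 | 0% |

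- Missing-day rule: an endoscopy E days before Day 1 removes the days E, E − 1 and E − 2 before Day 1. All 3 pre-dose days remain usable when E − 2 ≥ 4, that is E ≥ 6.
- If W0 were Visit 2 itself, D would be 0 and no pre-dose day could enter.
- SF and RB with Visit 3 on Day 5: the most recent 3 days are Days 2–4, all post-dose. Pre-dose days enter only if post-dose entries are missing. The averaged items and the Bristol maximum take them in directly.

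**The case against.** The best case for leaving this alone is that neither row is an input to a named efficacy endpoint. The diary-based endpoints are set at Week 12 and Week 52, and those windows are correct. Week 27 is not a visit: its row carries no visit number, and the schedule goes from Visit 16 (Week 26) to Visit 17 (Week 28). The appendix states the 7-day length repeatedly, so a careful programmer would notice the slip. The Week 1 row has the same form as Week 2 and does keep Week 1 from overlapping the Baseline window, which ends the day before W0. Its fault comes from the footnote's definition of W0 and appears only when Visit 3 is early. All of this stands, and it keeps the point minor. It does not make the printed cells right.

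Two stronger readings are tempting, and the documents support neither.

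- *A reader might infer that Week 27 makes the unstructured MMRM covariance near-singular.* The SAP does not say that between-visit weeks enter the model; its factor is visit. SF and RB, the items that can be exact copies, are not among the continuous secondary endpoints. For an averaged item, Week 27 would be a 14-day mean. Assuming equal variances, complete data and week-to-week correlation r, its correlation with Week 28 is √((1 + r)/2). That is 0.87, 0.95 and 0.97 for assumed r of 0.5, 0.8 and 0.9, which is high but not singular. If all 52 weeks did enter, the matrix would have 52 × 53/2 = 1,378 parameters for about 200 participants, so dimension would be the problem rather than this row. Fallback structures are already specified.
- *A reader might infer that the Week 1 treatment effect shrinks by up to 43%.* That share is the worst case for one participant. The documents give no frequency of early Visit 3, and the share does not describe SF, RB or a maximum such as Bristol.

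**Conclusion.** Both rows need correcting, and the severity is minor. The Week 27 fault follows from the printed table alone: 14 days at nominal visits, 8 to 14 within tolerance, always containing Week 28. The Week 1 fault rests on reading the footnote literally, on Visit 3 falling on Day 5 to 7, and on W0 being early enough. Three days is the most that the ±3 tolerance allows.

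What is affected is the weekly reporting of diary items at Weeks 1 and 27. The primary endpoint window and the Week 12 and Week 52 windows are untouched, and no harm to MMRM convergence is shown. One indirect route remains. SAP 6.6 fills a missing baseline from the first available postbaseline week, starting with Week 1. Inclusion Criterion 6 requires three days of SF and RB diary data before the screening endoscopy, so this should be uncommon for those two items.

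**What to change.** Change two cells in the SAP 6.6 table.

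1. Week 27 End Day: Week 28 visit date minus 8. The nominal window becomes Days 183–189, with no overlap with Week 28.
2. Week 1 Start Day: the later of the date of first dose and the Week 1 visit date minus 7. No pre-dose day can then enter. Leave the footnote as it is, because the Baseline row needs the endoscopy-based Week 0 date: SAP 4.1 builds baseline MMS from diary entries before the screening endoscopy.

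The cost is a short SAP edit before unblinding, with one small trade-off. With Visit 3 on Day 5 the Week 1 window has exactly 4 days (Days 1–4), so a single missed entry makes the six items that need 4 days missing at Week 1. The SAP should acknowledge this.

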Tuberculosis (TB) test	X									Patients who had a tuberculin skin test (TST) will return from 48 to 72 hours after placement to have the test result read. Samples may be sent to central or local laboratory based on the type of test. A local laboratory must be qualified by local regulations.
Human immunodeficiency virus (HIV) screening tests	X									
Hepatitis C virus (HCV) screening tests	X									HCV RNA will be measured to confirm positive hepatitis C virus antibody.
Hepatitis B virus (HBV) screening tests	X									Includes testing for HBsAg and anti-HBc.

Table 1. Schedule of Activities for the Screening and Induction Treatment Periods of Study J1P-MC-KFAH										
V1 and V9 procedures may be conducted over more than 1 day as long as all activities are completed within the allowable visit tolerance and all scheduled activities are completed prior to dosing.										
For procedures at an ETV, see ETV in Table 4.										
For procedures at an unscheduled visit, see V997 in Table 4.										
Visit number	V1	V2	V3	V4	V5	V6	V7	V8	V9	Comment
Weeks from randomization	-5	—	1	2	4	6	8	10	12	
Study day	—	1	8	15	29	43	57	71	85	
Visit interval tolerance (days)	≤35 before V2	—	±3	±3	±3	±3	±3	±3	±3	
Fasting visit		X							X	
HBV DNA	X								X	Only for participants who are positive for anti-HBc at screening.
Pharmacokinetic (PK) samples		X	X	X	X		X		X	Collect samples before dosing, if dosing is scheduled. Collect additional samples at specified times relative to onset of hypersensitivity events.
CCI		X		X	X		X		X	Collect samples before dosing, if dosing is scheduled. Collect additional samples at specified times relative to onset of hypersensitivity events.
Flow cytometry panel		X		X					X	
Genetics sample		X								Blood sample for DNA pharmacogenetics can be obtained any time at or after V2.
CCI		X			X		X		X	
Endoscopic Procedure										
Endoscopy	X								X	Screening endoscopy must occur ≤14 days prior to randomization. At screening, perform only for participants who are eligible for the study by all other study entry criteria.
Colon biopsy sample collection	X								X	Performed at time of endoscopy. Instructions for collection are provided in the lab manual. Flexible sigmoidoscopy is recommended, except for protocol-specified reasons when a colonoscopy should be performed.

Table 1. Schedule of Activities for the Screening and Induction Treatment Periods of Study J1P-MC-KFAH										

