5.1. Inclusion Criteria

Patients with UC will be included in the study only if they meet all of the following inclusion criteria.

Informed Consent

1. Are capable of giving informed consent as described in [Appendix 1](#), Section 10.1.3, which includes compliance with the requirements and restrictions listed in the ICF and in this protocol, including the contraception requirements.

Note: For the contraception requirements of this protocol, see [Appendix 4](#). Contraceptive use by men or women should be consistent with local regulations regarding the methods of contraception for those participating in clinical studies.

Patient Characteristics

2. Are male or female patients from 18 to 75 years of age, inclusive, at the time of initial screening (Visit 1).

Note: Women of child-bearing potential (WOCBP) must test negative for pregnancy as indicated by a negative serum pregnancy test at the screening visit followed by a negative urine pregnancy test within 24 hours prior to first exposure to study drug.

3. Have venous access sufficient to allow the protocol-required blood sampling.
4. Are willing and able to complete the scheduled study assessments, including endoscopies and daily diary entries.

Disease-Specific Characteristics

5. Have had an established diagnosis of UC of ≥ 3 months in duration before baseline (Visit 2), which includes endoscopic evidence of UC and a histopathology report that supports a diagnosis of UC (see Section 8.1.1.3). Supportive endoscopy and histopathology reports must be available in the source documents.
6. Have moderately to severely active UC as defined by a modified Mayo score (MMS) of 4 to 9 with an endoscopic subscore (ES) ≥ 2 , with endoscopy performed within 14 days before baseline.

Note: The MMS requires accurate documentation of the stool frequency (i.e. baseline prior to onset of UC signs/symptoms OR stool frequency when in remission) as well as

3 days of diary data (of stool frequency and rectal bleeding) in the 7 days preceding the first date of bowel prep, if no bowel prep, day of endoscopy).

Note: The Mayo ES, as determined by the Image Review charter, will be provided to the site prior to randomization to enable determination of the MMS for eligibility.

7. Have evidence of UC extending proximal to the rectum (with ≥ 15 cm of involved colon).
8. Have documentation of
 - 8a. a surveillance colonoscopy (performed according to local standard) within 12 months before baseline for

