4.1. General Considerations

This SAP is intended to describe the analyses of all objectives, as well as safety assessments, for study KFAH.

Statistical analysis of this study will be the responsibility of Eli Lilly and Company (hereafter Lilly) or its designee. For primary and key secondary objectives, statistical analyses will be performed using SAS® Enterprise 7.1 or higher, SAS® Version 9.4 or higher, or RStudio Server Pro Version R.3.6.3. or higher.

Efficacy analyses will be conducted on the mITT population. Safety analyses will be conducted on the Safety population (same as mITT population, as described in Section 3). The efficacy analysis of the primary endpoint and secondary endpoints will be repeated for ITT population. Additional safety analyses may be performed as deemed appropriate.

The baseline modified Mayo Score (MMS) is calculated from valid daily diary entries obtained prior to endoscopy during the screening period and the endoscopic appearance of the mucosa at this screening endoscopy. For other efficacy, health outcome and safety assessments, baseline is defined as the last non-missing assessment recorded on or prior to the date of the randomization visit (Visit 2).

Any change to the data analysis methods described in the protocol will require an amendment ONLY if it changes a principal feature of the protocol. Any other change to the data analysis methods described in the protocol and the justification for making the change will be described in the clinical study report. Additional exploratory analyses of the data will be conducted as deemed appropriate.

Not all displays and analyses described in this SAP will necessarily be included in the CSR. Not all displays will necessarily be created as a “static” display. Some displays may be incorporated as interactive display tools instead of or in addition to a static display. Any display described in this SAP and not provided in CSR would be available upon request.

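### SAP Appendix 6 fills a missing PRO diary baseline with a post-dose score before trying other pre-dose days, and rounds five weekly PRO means to integers: minor, but cheap to correct

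*SAP*

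**What the plan says.** **Baseline definition.** Apart from the modified Mayo score, SAP 4.1 defines baseline as the "last non-missing assessment recorded on or prior to the date of the randomization visit (Visit 2"). Protocol 9.4.1 has the same definition.

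**Diary scoring (SAP 6.6).** The baseline week is the 7 days before the Week 0 visit date. That date is taken first from the screening bowel preparation, then from the endoscopy. For stool frequency (SF) and rectal bleeding (RB), "Patients with less than 3 measurements in the 7 day period will be considered missing". For Bristol and the other diary items, "If fewer than 4 days are available (i.e., not missing), the patient will be considered to be missing data for that week". If the baseline is missing under these rules, "the first available postbaseline assessment starting with Week 1 will be used to impute the baseline so that the patient can be included". There is no step that first looks for other pre-dose days.

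**Rounding (SAP 6.6).** For diary items other than SF, RB and Bristol, "all available days of the 7 days will be averaged and rounded to the nearest integer to calculate the weekly score for each patient". Bristol uses a weekly maximum. IBDQ is not a diary item.

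**Entry.** The note to Inclusion Criterion 6 requires "3 days of diary data (of stool frequency and rectal bleeding) in the 7 days preceding the first date of bowel prep". The Schedule of Activities dispenses the diary at Visit 1 and states: "Screening endoscopy must occur ≤14 days prior to randomization".

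**The concern.** For a participant whose baseline is imputed, an outcome value becomes the reference for change and also a covariate in the MMRM of SAP 4.1.1. If Week 1 supplies the value, that participant's Week 1 change is exactly zero. Any drug effect already present in the imputing week is subtracted from the later effect. The same value enters the unadjusted change summaries and plots (SAP 4.4.2) and mBOCF (SAP 4.1.2.3).

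Six of the seven secondary PROs are exposed, all but IBDQ. The trigger is built in, because entry needs 3 diary days and a PRO baseline needs 4. Pre-dose data that would meet the SAP 4.1 definition may be on file and go unused.

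Rounding is a separate matter. It discards resolution in the weekly means of urgency, abdominal pain, fatigue, PGR-S and nocturnal stools, and the plan gives no reason for it.

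**Working it through.** The plan gives no diary completion rate, PRO standard deviation, correlation or onset time, and no PRO power. Its power figures concern clinical remission, so there is no plan figure to reproduce here. Every such input below is an assumption.

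**1. Trigger.** With independent daily completion c, the share of eligible entrants with exactly 3 of 7 days is P(X = 3) / P(X ≥ 3), X ~ Binomial(7, c).

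| c | P(X = 3) | P(X ≥ 3) | Share f | Per 40 | Per 200 |
|---|---|---|---|---|---|
| 90% | 0.00255 | 0.99982 | 0.26% | 0.1 | 0.5 |
| 80% | 0.02867 | 0.99533 | 2.88% | 1.2 | 5.8 |
| 70% | 0.09724 | 0.97120 | 10.0% | 4.0 | 20.0 |

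The 70% row is the least likely, given the entry criteria on diary use and the compliance check at each visit.

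**2. Unused pre-dose days.** With the endoscopy k days before Visit 2, and the endoscopy day and the two days after it excluded, k − 3 usable days remain before Visit 2: 11 at k = 14, 4 at k = 7, 2 at k = 5, none at k ≤ 3. Earlier screening days may also exist.

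**3. The Week 1 window.** It starts at "Max(Week 0 Visit Date, Week 1 Visit Date – 7") and ends the day before Visit 3. For Visit 3 on Day 5 to Day 11 it holds 3, 4, 5, 6, 7, 7 and 7 days after the dosing day (6 at the nominal Day 8). With Visit 3 on Day 5 it also holds 3 days before dosing, so it is not always wholly post-dose.

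**4. Bias at Week 12.** Let d be the effect already present in the imputing week, and b the slope of the Week 12 score on baseline. Imputation shifts the active arm's mean baseline by f × d relative to placebo. The bias toward zero is then about f × d for unadjusted change and b × f × d after baseline adjustment.

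Assume a true Week 12 effect of 1 point, SD 2.5, d = 0.2 or 0.5, and b = 0.5:
- f = 2.88%: 0.5 × 0.0288 × 0.5 = 0.007
- f = 10%: 0.5 × 0.10 × 0.5 = 0.025

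An MMRM simulation (visits at Weeks 1, 2, 4, 8 and 12, unstructured covariance, about 14% dropout at random, baseline correlations from 0.70 at Week 1 to 0.50 at Week 12) gave:

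| f | MMRM bias, d = 0.2 / 0.5 | Unadjusted bias, d = 0.2 / 0.5 |
|---|---|---|
| 0.26% | 0.0002 / 0.0007 | 0.0004 / 0.0013 |
| 2.88% | 0.0024 / 0.0070 | 0.0048 / 0.0137 |
| 10% | 0.0102 / 0.0248 | 0.0195 / 0.0475 |

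The simulated standard error of the Week 12 difference was 0.526 (40 v 40) and 0.435 (80 v 40).
- At 80% completion: 0.0070/0.526 = 1.3% and 0.0070/0.435 = 1.6% of one SE.
- Worst assumed case: 0.0248/0.526 = 4.7% and 0.0248/0.435 = 5.7% of one SE.

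A separate single-visit simulation with inputs outside this range (20% imputed, d = 0.6, true effect 1.5) tests the formulas. They predict 1.5 − 0.12 = 1.38 unadjusted and 1.5 − 0.06 = 1.44 adjusted. It returned 1.38 and 1.44.

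**5. Rounding.** Rounding adds about 1/12 to the variance s² of each weekly score. With a baseline to follow-up correlation of 0.5, the residual variance goes from 0.75s² to (s² + 1/12) − (0.5s²)²/(s² + 1/12).

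| SD | Residual variance | SE | 40 patients worth |
|---|---|---|---|
| 1 | 0.750 → 0.853 (+13.7%) | +6.6% | 35.2 |
| 2 | 3.000 → 3.104 (+3.5%) | +1.7% | 38.7 |
| 3 | 6.750 → 6.854 (+1.5%) | +0.8% | 39.4 |

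**The case against.** **Appendix 6 can be read as a supplement to SAP 4.1.** It applies only when the defined week yields no score, its stated purpose is to keep the patient in the analysis, and Protocol 8.1.1.2 leaves the details of diary analysis to the SAP. A reader might infer a flat contradiction that voids the rule; the documents do not go that far. Still, a supplementary reading does not explain why pre-dose days that would meet SAP 4.1 are skipped. Nor does the SAP flag a departure: its Introduction reports no changes to the protocol's analyses, while Protocol 9.4.1.2 rules out additional imputation for the MMRM.

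**The bias is small and rests on assumptions.** This stands. It also needs an early drug effect, and no multiplicity-controlled claim depends on these endpoints.

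**A reader might infer that the primary endpoint is affected.** Read literally, the imputation sentence also covers SF and RB. But both are scored with the 3-of-7 threshold used for entry, so an eligible participant should rarely trigger it, and no effect on clinical remission has been shown.

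**A reader might infer that the rule favours the drug.** With equal missingness across arms it does the reverse.

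**Integer scores keep the instruments' scale.** SAP 4.1.1 asks for analysis on the measured scale, but a mean of 4 to 7 daily scores is on that scale without being an integer. It remains true that rounding contradicts no part of the plan, and that the 6.6% figure needs an assumed SD of 1.

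**An open-ended look-back could do harm.** This stands. Screening lasts up to 35 days, while Inclusion Criterion 10 and Exclusion Criterion 19 require stable 5-ASA and corticosteroid doses, and several washouts, only for the 2 weeks before the screening endoscopy. Any look-back therefore needs an earliest date.

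**Conclusion.** The point holds as a minor improvement for the secondary diary PROs. SAP 6.6 moves from a missing baseline week to a post-baseline score without trying other pre-dose days, which is out of line with the baseline definition in SAP 4.1 and Protocol 9.4.1. The 3-day and 4-day thresholds make this reachable for eligible participants.

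At Week 12 the MMRM bias is under 0.1% of the effect at 90% completion, 0.2–0.7% at 80% and 1.0–2.5% at 70%, if 20–50% of the effect is already present in the imputing week. In unadjusted change it is about twice as large. The reading of the text is secure; the sizes depend on assumed completion, SD, correlation and onset. The argument for the edit is that a pre-dose baseline can be restored at little cost, not that PRO conclusions are at risk.

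The rounding is a separate, avoidable loss of precision, negligible for items with an SD of 2 to 3 and noticeable only for an item with an SD near 1.

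**What to change.** **(1) Replace the imputation sentence in SAP 6.6 for non-Mayo diary items.**
- If the baseline week has fewer than 4 valid days, score the baseline from the latest valid diary days before the first dose, using 7 if available and at least 4.
- Use no day earlier than 14 days before the screening endoscopy. Exclude bowel-preparation days, the endoscopy day and the two days after it.
- Never use a post-dose value as baseline.
- If too few days remain, use the pooled all-arm baseline mean as that participant's baseline in the MMRM only. Leave the participant out of descriptive change summaries and mBOCF, and report how many are affected.
- List the rule in SAP 4.9, because Protocol 9.4.1.2 allows no additional imputation in the MMRM.
- Leave SF and RB scoring unchanged.

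**(2) Delete the integer rounding** for urgency, abdominal pain, fatigue, PGR-S and nocturnal stools. Keep it for SF and RB.

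**Cost.** Two SAP sentences, the SAP 4.9 entry and minor programming; the MMRM specification stays as planned. A few participants have a slightly different pre-dose window, and denominators differ slightly between displays.

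The last resort should be rare. A participant with 3 days needs one more, and post-endoscopy days alone fail to supply it with probability (1 − c)^(k − 3):
- At 70% completion: 0.3² = 9.0% at k = 5 and 0.3⁴ = 0.8% at k = 7, or about 1.8 and 0.2 of 200 participants.
- At 80% completion: 4.0% and 0.16%, or about 0.2 and 0.01 of 200.

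Eligible days before the baseline week would lower these counts. Even when applied to every triggered participant in the same simulation, the pooled mean gave a Week 12 bias between −0.0007 and +0.0007 points.
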